## 2. Outcomes

- a. Effectiveness endpoint:
  - i. Primary: a composite of all-cause death or HF hospitalization
    - Note cardiovascular death was not used because National Death Index data were only available up to 2016. Instead, all-cause death was used.
    - HF hospitalization is defined as HF diagnosis primary position in the inpatient dataset
  - ii. Secondary: individual components separately
- b. Safety endpoint:
  - i. Primary: a composite of SAE, defined as any hospitalization or ED visit due to diagnosis codes in the primary position:
    - hypotension
    - acute kidney injury/acute kidney failure
    - hyperkalemia
    - angioedema
  - ii. Secondary: individual components

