## BACKGROUND

1. Angiotensin receptor blocker neprilysin inhibitor (ARNI) sacubitril/valsartan (Entresto (1))
  - a. Approved in July 7, 2015
  - b. Indication: HF with reduced ejection fraction
2. PARADIGM-HF trial; ARNI vs enalapril (2)
  - a. N=8442, follow-up 2.3 years
  - b. Composite of cardiovascular death and HF hospitalization: 21.8% vs 26.5%
  - c. Safety endpoints: hypotension (14.0% vs 9.2%), renal failure (3.3% vs 4.5%), hyperkalemia (16.1% vs 17.3%), angioedema (0.4% vs 0.2%)
3. 2017 ACC/AHA/HFSA guidelines for management of heart failure (3)
  - a. The clinical strategy of inhibition of the renin-angiotensin system with ACE inhibitors (Level of Evidence: A), OR ARBs (Level of Evidence: A), OR ARNI (Level of Evidence: B-R) in conjunction with evidence-based beta blockers, and aldosterone antagonists in selected patients, is recommended for patients with chronic HFrEF to reduce morbidity and mortality.
  - b. The use of ACE inhibitors is beneficial for patients with prior or current symptoms of chronic HFrEF to reduce morbidity and mortality (Level of Evidence: A). Although the use of an ARNI in lieu of an ACE inhibitor for HFrEF has been found to be superior, for those patients for whom ARNI is not appropriate, continued use of an ACE inhibitor for all classes of HFrEF remains strongly advised.
  - c. The use of ARBs to reduce morbidity and mortality is recommended in patients with prior or current symptoms of chronic HFrEF who are intolerant to ACE inhibitors because of cough or angioedema (Level of Evidence: A). Head-to-head comparisons of an ARB versus ARNI for HF do not exist. For those patients for whom an ACE inhibitor or ARNI is inappropriate, use of an ARB remains advised.
  - d. In patients with chronic symptomatic HFrEF NYHA class II or III who tolerate an ACE inhibitor or ARB, replacement by an ARNI is recommended to further reduce morbidity and mortality (Level of Evidence: B).

- e. ARNI should not be administered concomitantly with ACE inhibitors or within 36 hours of the last dose of an ACE inhibitor (Level of Evidence: B). Oral neprilysin inhibitors, used in combination with ACE inhibitors can lead to angioedema and concomitant use is contraindicated and should be avoided.
- f. ARNI should not be administered to patients with a history of angioedema (Level of Evidence: C).

4. 2021 ACC/AHA/HFSA focused update (4)

[figure not shown]

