## **STUDY OVERVIEW AND DESIGN**

- 1. Study aims: To emulate a prospective surveillance of the effectiveness and safety of ARNI vs a comparator (ARB) in older adults with HFrEF and different frailty status.
- 2. Data source(s): Data from 2014 up to 2020 will be used.
  - a. Medicare Database
  - b. Optum Database
  - c. MarketScan Research Database
- 3. Sequential cohort monitoring design (see Figure 1): The monitoring analysis will include 1) retrospective analysis of available data (2015-2017) at the time of first analysis (January 2021) and 2) prospective analysis of new data (2018-2020) as they become available to the researchers. Within each database, we will emulate biannual updating of data by creating a propensity score (PS)-matched cohort of new users every 6-month interval, beginning on the first marketing of ARNI (July 7, 2015-December 31, 2015, and 6-month intervals afterwards). Each sequential cohort will be followed for development of the outcomes of

interest. Outcome analysis will be performed at a pre-specified 6-month interval (prospective analysis). The surveillance will be performed by frailty status (frail vs non-frail) at the time of drug initiation. The results from each database will be pooled using fixed-effects meta-analysis (assuming low heterogeneity across the databases).

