## STATISTICAL ANALYSIS

### **Estimation of treatment effectiveness and safety within each database**

1. PS-matched cohorts: Within each surveillance cohort by frailty status (frail vs non-frail), we will use logistic regression that estimates the probability of receiving the drug of interest as a function of sociodemographic characteristics, diseases, prescription drugs, comorbidity index, and frailty index. Note that PS model will be fit separately by frailty status. We will perform a 1:1 ratio nearest-neighbor PS matching, with a caliper of 0.2 of the standard deviation of the logit PS (9). We will evaluate balance in covariates using standard mean difference (<0.1 is considered adequate balance) within each surveillance cohort.
2. Primary analysis for effectiveness and safety: For time-to-event analysis of the effectiveness and safety endpoints, we will use Cox proportional hazards regression to estimate the hazard ratios (HR) and 95% confidence intervals (CI) by frailty status (frail vs non-frail). The follow-up will begin on day 1 and end on the day of development of the effectiveness or safety endpoints or the earliest of the following censoring events: switching or discontinuation of the study drug, death not due to the outcome of interest, disenrollment, and end of data period (see Figure 2). Proportional hazards assumptions will be checked using Schoenfeld residuals.
3. Subgroup analyses for primary effectiveness and safety endpoints will be conducted by frailty status (frail vs non-frail):
  - a. age (65-74 years vs  $\geq 75$  years)
  - b. sex
  - c. race (black or non-black)
  - d. dual eligibility for Medicaid
  - e. major multimorbidity burden/pattern (informed by latent class analysis)
  - f. dementia (CCW definition)
  - g. HF hospitalization status ( $\geq 2$  or  $< 2$  in the past year)

4. Secondary analyses will be conducted by frailty status (frail vs non-frail):
  - a. secondary endpoints (individual components of primary effectiveness and safety composite endpoints)
5. Sensitivity analysis for primary effectiveness and safety endpoints will be conducted by frailty status (frail vs non-frail):
  - a. “intention-to-treat” analysis with a maximum follow-up time of 1 and 2 years from the index date
  - b. exposure risk window or grace period of 14 days

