6. Adjustment for multiple testing in detecting signal: We will use the maximum sequential probability ratio testing (maxSPRT) procedure to keep the overall type-1 error rate of 0.05.  
(10)

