#### **Estimation of the pooled treatment effectiveness and safety**

7. The treatment effect estimates from 3 databases will be combined using meta-analysis techniques. We will examine the heterogeneity of treatment effect using Cochrane Q statistics and I-square statistics. If there is no statistically significant evidence of treatment effect heterogeneity, we will use inverse probability fixed-effects model to pool the database-specific estimates. If there is significant treatment effect heterogeneity, we will use random-effects model.
8. Reporting of prospective monitoring results: When a statistically significant signal is detected from the pooled analysis for the primary endpoints of effectiveness or safety from pre-specified interim analysis or at the end of the data period (12/31/2020), the findings will be reported

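### Does tying the 6-month safety report to the four-part composite leave a hypotension excess without a trigger?

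*Protocol*

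**What the plan says.** - **Primary safety endpoint** (Protocol, MEASUREMENTS, 2. Outcomes, b): "a composite of SAE, defined as any hospitalization or ED visit due to diagnosis codes in the primary position", covering hypotension, acute kidney injury or failure, hyperkalemia and angioedema. Each component is also a secondary endpoint.
- **Component analyses** (STATISTICAL ANALYSIS, item 4): "secondary endpoints (individual components of primary effectiveness and safety composite endpoints") are analysed separately in frail and non-frail patients.
- **Look schedule** (STUDY OVERVIEW AND DESIGN, item 3): "Outcome analysis will be performed at a pre-specified 6-month interval (prospective analysis").
- **Error control** (STATISTICAL ANALYSIS, item 6): under "Adjustment for multiple testing in detecting signal", maxSPRT holds the overall type-1 error at 0.05. No endpoint is named.
- **Reporting rule** (STATISTICAL ANALYSIS, item 8): a report follows "When a statistically significant signal is detected from the pooled analysis for the primary endpoints of effectiveness or safety from pre-specified interim analysis". The same item also provides for a report when data collection closes on 12/31/2020.
- **Background rates** (BACKGROUND, item 2.c, ARNI vs enalapril): "hypotension (14.0% vs 9.2%), renal failure (3.3% vs 4.5%), hyperkalemia (16.1% vs 17.3%), angioedema (0.4% vs 0.2%)." Item 3.c of the same section adds, on the comparator actually used: "Head-to-head comparisons of an ARB versus ARNI for HF do not exist".

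**The concern.** Read together, outcomes items 2.b.i and 2.b.ii and statistical items 4 and 8 make the composite the only safety endpoint whose signal obliges a report at an interim look. The effectiveness composite can also trigger one, but it says nothing about hypotension. The Protocol's background figures move in different directions: hypotension and angioedema are higher on ARNI, renal failure and hyperkalemia lower. Adding components that move in opposite directions pulls the composite ratio towards 1, so a real excess of hypotension might pass several looks without a signal. In a study whose aim is surveillance of safety by frailty status, that would be a loss of timeliness. The apparent remedy is to give hypotension its own sequential test with a share of the error rate.

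**Working it through.** The Protocol states no sample size, event count or power, so there is no figure of its own to reproduce. The check asks how large the dilution could be, and whether a separate trigger would clearly be better.

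**Inputs.** Component risks come from BACKGROUND item 2.c and 1:1 matching from STATISTICAL ANALYSIS item 1. Assumed: 80% power, two-sided 0.05 and a single fixed look. A maxSPRT boundary would raise all the counts.

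**1. Component ratios**

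| Component | ARNI vs enalapril (%) | Ratio |
|---|---|---|
| Hypotension | 14.0 / 9.2 | 1.52 |
| Renal failure | 3.3 / 4.5 | 0.73 |
| Hyperkalemia | 16.1 / 17.3 | 0.93 |
| Angioedema | 0.4 / 0.2 | 2.0 |
| Last three summed | 19.8 / 22.0 | 0.90 |

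**2. Composite ratio**
- Summed, no overlap: 33.8 / 31.2 = 1.083.
- Independent components: 30.51 / 28.43 = 1.073.
- Renal failure wholly inside hyperkalemia: 30.5 / 26.7 = 1.142.

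**3. Patients needed, relative to hypotension alone.** There are two ways to compute this.
- *Events formula:* events = 4(1.960 + 0.842)² / (ln ratio)², divided by mean risk. Hypotension needs about 178 events and the summed composite about 4,900. The patient ratio is (4,900 / 0.325) / (178 / 0.116) = 9.8. Independence gives 14.0 and nesting gives 4.0. This treats a risk ratio as a hazard ratio, which holds only for rare events, and these risks are near 30%.
- *Two-proportion formula*, which suits such risks: 698 per arm for hypotension, 5,094 for the summed composite and 7,575 under independence. The ratios are 5,094 / 698 = 7.3 and 7,575 / 698 = 10.9. Nesting gives about 3.2.

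On the cited rates the dilution is therefore real, at roughly 3 to 11 times.

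**4. Dependence on the event mix.** Let s be the share of comparator-arm composite events that are hypotension and q the ratio for the rest. The composite ratio is s × 1.522 + (1 − s) × q.

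| s | q | Composite ratio |
|---|---|---|
| 0.16 | 0.90 | 1.00 |
| 0.295 | 0.90 | 1.08 |
| 0.295 | 1.00 | 1.15 |
| 0.295 | 1.10 | 1.22 |
| 0.50 | 0.90 | 1.21 |
| 0.50 | 1.00 | 1.26 |
| 0.80 | 1.00 | 1.42 |

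The Protocol gives neither s nor q for primary-position hospital or ED events against an ARB. The result runs from full cancellation to almost none.

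**5. Price of a separate trigger.** The required events scale with (z + 0.842)².
- With 0.04 for the composite and 0.01 for hypotension, the composite needs about 7% more events. With 0.025 each, it needs 21% more.
- Hypotension tested at 0.01 needs about 265 events instead of 178, a factor of 1.49.
- By the events formula, hypotension at 0.01 is no quicker than the composite at 0.05 once s exceeds about 0.63 (q = 1) or 0.73 (q = 0.90). At s = 0.295 the same holds once q reaches about 1.09.
- Unadjusted triggers on the composite and all four components would give 1 − 0.95⁵ = 0.23 if the tests were independent.

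**6. Calendar.** The Protocol is dated 01/14/2021 and the data period ends on 12/31/2020. STUDY OVERVIEW AND DESIGN describes emulated surveillance: 2015-2017 is analysed retrospectively in January 2021, and 2018-2020 as the data reach the researchers. All exposure and events in the data period had occurred before the plan was written.

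**The case for a change.** The strongest case for the concern is that the direction of dilution does not depend on the cited rates. Whenever the other components are neutral or lower on ARNI, the composite ratio lies closer to 1 than the hypotension ratio. Timeliness is the reason for having 6-month looks. Hypotension is also the common harm that rose in the one trial the Protocol cites, and the amendment would be a few words with a stated error share.

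The reading of item 8 and the direction of dilution both stand. Three things do not carry over.

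- **Item 8 obliges a report; it forbids none.** It says when findings will be reported. It does not bar reporting a component result, and item 6 does not confine maxSPRT to the composite. Which secondary endpoints receive a sequential boundary is commonly settled in a statistical analysis plan, which is not at hand.
- **The reason for choosing hypotension is weak here.** It rests on rates against enalapril that lack the primary-position hospital or ED restriction. STUDY POPULATION, item 3.h, also excludes patients with recent hypotension, acute kidney injury or hyperkalemia, which may change the mix again.
- **The benefit is uncertain and the cost is not.** The composite loses sensitivity in every case, while the gain for hypotension disappears in several plausible mixes.

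**Conclusion.** The concern does not hold as a fault in the plan. The Protocol defines a coherent composite, analyses every component by frailty status, schedules outcome analysis every 6 months and reports at the end of data whatever the signals show. Following it as written gives no wrong estimate and no inflated error rate, and no component result is lost. Whether to spend part of the error rate on hypotension is a trade-off on which experienced statisticians would differ.

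The dilution could be large on the cited rates (composite ratio 1.07 to 1.14; about 3 to 11 times the patients by two proportions). It could also be small if hypotension dominates or the other components also rise. These figures assume a fixed look at two-sided 0.05 with 80% power, and rates that may not apply against an ARB. The one possible loss is a delay in reporting a hypotension signal while data releases are awaited. The Protocol does not state that lag, so the delay cannot be sized, but it affects no exposure or event within the data period.

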## 3. Covariates

- a. Sociodemographic information: age, sex, race, dual eligibility
- b. Diseases: Chronic Conditions Data Warehouse (CCW) chronic conditions (see Table 2), provided in the Medicare Beneficiary Summary File (first date of satisfying the claims-based algorithm for individual conditions is available; considered present if this date is earlier than the index date)
- c. Prescription drugs: ATC3 classes with prevalence threshold  $>1\%$  in a representative Medicare sample
- d. Gagne combined comorbidity score (6)
- e. Claims-based frailty index (7): Frailty status will be defined as non-frail if  $<0.20$  or frail if  $\geq 0.20$

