**Table 2. CCW Chronic Conditions (8)**

Acquired Hypothyroidism	Chronic Kidney Disease
Acute Myocardial Infarction	Chronic Obstructive Pulmonary Disease
Alzheimer's Disease, Related Disorders, or Senile Dementia	Depression
Anemia	Diabetes
Asthma	Glaucoma
Atrial Fibrillation	Hip / Pelvic Fracture
Benign Prostatic Hyperplasia	Hyperlipidemia
Cancer (any of the following): Cancer, Colorectal Cancer, Endometrial Cancer, Breast Cancer, Lung Cancer, Prostate	Hypertension
	Ischemic Heart Disease
	Osteoporosis
	Rheumatoid Arthritis / Osteoarthritis
	Stroke / Transient Ischemic Attack
Cataract	

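### Acute Table 2 conditions are coded only by first-ever date, so matching and the balance check cannot see recent or recurrent myocardial infarction or stroke

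*Protocol*

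**What the plan says.** The Protocol, MEASUREMENTS, 3. Covariates, item b, takes disease covariates from the Chronic Conditions Data Warehouse list in Table 2 and states the coding rule: "first date of satisfying the claims-based algorithm for individual conditions is available; considered present if this date is earlier than the index date". The rule has no lower time limit, no term for time since the event and no use of later occurrences.

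Most Table 2 entries are chronic, but the list also contains "Acute Myocardial Infarction", "Stroke / Transient Ischemic Attack", hip/pelvic fracture and several cancers, all under the same rule.

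STATISTICAL ANALYSIS, item 1, models the probability of treatment "as a function of sociodemographic characteristics, diseases, prescription drugs, comorbidity index, and frailty index", separately by frailty status, and matches 1:1. On diagnostics it says: "We will evaluate balance in covariates using standard mean difference (<0.1 is considered adequate balance) within each surveillance cohort".

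STUDY POPULATION, item 3, has exclusions tied to the 60 days up to the index date: HF hospitalization (3.e), nursing facility stay (3.f), and hypotension, advanced kidney disease or dialysis, acute kidney injury and hyperkalemia (3.h). Myocardial infarction and stroke are not among them.

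**The concern.** For a chronic disease, having met the definition at any earlier time is a reasonable description of status at drug start. For an acute event it describes history only. A recent infarction or stroke plausibly raises the short-term risk of death or HF hospitalization, the primary effectiveness endpoint. It may also influence whether a clinician chooses a newly marketed drug or an older class. A factor linked to both treatment and outcome should be in the matching model, or at least be visible in the balance table.

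Under the stated rule it is in neither. If recent events are unevenly distributed between the matched arms, the hazard ratio keeps that confounding while the table reports good balance on the ever-flag. Repeated looks and pooling over databases would not remove such a shift.

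The Protocol itself treats recency as informative elsewhere: it uses 60-day windows for exclusions and defines a subgroup by HF hospitalizations in the past year (STATISTICAL ANALYSIS, item 3.g).

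**Working it through.** The Protocol states no figure on this point, so there is none to reproduce. The check is a reading of the rule, followed by an illustration on assumed inputs.

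**1. What the rule does to four patients** (the rule is in 3. Covariates, item b)

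| Infarction history before the index date | First date earlier than index? | Coded value |
|---|---|---|
| One event, 30 days before | yes | 1 |
| One event, several years before | yes | 1 |
| First event years before, second 30 days before | yes | 1 |
| None | no | 0 |

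The first three patients cannot be told apart. The third shows that a recurrence adds nothing once a first date exists. Stroke/TIA behaves in the same way.

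**2. Whether anything else in the plan dates the event**

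- Propensity score inputs: sociodemographics, Table 2 flags, drug classes, comorbidity score and frailty index. The last three may correlate with a recent event. The text gives no assessment windows for them and the design figure is not available, so how recent the status they capture is cannot be judged. None of them identifies the timing of an infarction or stroke.
- Exclusions: item 3.f removes patients with a recent nursing facility claim, which will take out some with a recent stroke or hip fracture. Items 3.e and 3.h remove other recent events. None removes a recent infarction or stroke as such.
- Balance check: it applies to the covariates as defined, and so to the ever-flag.

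**3. Illustration** (every prevalence and multiplier below is an assumption)

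Let p1 and p0 be the proportions with a recent event among matched ARNI and ARB starters, and m its hazard multiplier.

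- SMD = |p1 − p0| / √{[p1(1 − p1) + p0(1 − p0)] / 2}
- Apparent hazard ratio when the true value is 1 ≈ [1 + p1(m − 1)] / [1 + p0(m − 1)]

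The second formula treats the recent event as the only unmatched factor and ignores any control through proxies.

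For p1 = 0.05, p0 = 0.10, m = 2:

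- SMD = 0.05 / √[(0.0475 + 0.0900) / 2] = 0.05 / 0.2622 = 0.191
- Apparent hazard ratio = 1.05 / 1.10 = 0.955

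Other values with p1 = 0.05:

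| p0 | SMD of recent event | m = 1.5 | m = 2 | m = 2.5 |
|---|---|---|---|---|
| 0.08 | 0.122 | 1.025/1.04 = 0.986 | 1.05/1.08 = 0.972 | 1.075/1.12 = 0.960 |
| 0.10 | 0.191 | 1.025/1.05 = 0.976 | 1.05/1.10 = 0.955 | 1.075/1.15 = 0.935 |
| 0.12 | 0.253 | 1.025/1.06 = 0.967 | 1.05/1.12 = 0.938 | 1.075/1.18 = 0.911 |

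A second parameterization holds the ever-flag exactly equal between arms. With ever-infarction at 30% in both, its SMD is 0. If the recent share is 10% in one arm and 20% in the other, recent infarction is 3% vs 6%, its SMD is 0.145, and with m = 2 the apparent hazard ratio is 1.03/1.06 = 0.972. So a perfect reading on the planned covariate is compatible with a failing reading on the unplanned one. Swapping the arms in the central example gives 1.10/1.05 = 1.048, so the direction is open too.

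**4. Look-back length**

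STUDY OVERVIEW AND DESIGN, item 2, says "Data from 2014 up to 2020 will be used". If first dates had to be built from those data alone, the longest look-back would be 552 days (1.5 years) for an index date of July 7, 2015 and 2,556 days (7.0 years) for December 31, 2020. But matching is done within a database and a 6-month interval, so both arms of any matched comparison have nearly the same maximum look-back.

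**The case against.** The strongest objection is that the gap is narrower than it looks and its effect is unproven. Most Table 2 conditions are chronic and the ever-flag suits them. The facility-stay exclusion removes many patients soon after a stroke or hip fracture, and the other 60-day exclusions remove further unstable patients. Drug classes, comorbidity score and frailty index all enter the propensity score. The illustrative prevalences are chosen, not observed, so an SMD above 0.1 follows from the choice and is no evidence of imbalance. A statistical analysis plan could also add covariates.

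Much of this stands and limits the point. Three stronger readings are tempting, and the document does not support them:

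- *No recent acute event is controlled.* Recent HF hospitalization, hypotension, acute kidney injury and hyperkalemia are handled by exclusion. The gap is chiefly myocardial infarction and stroke/TIA, and to a lesser extent hip/pelvic fracture and cancers.
- *The 1.5 versus 7.0 year look-back biases ARNI against ARB.* Those extremes belong to cohorts that are never matched to each other. The difference concerns what the flag means across cohorts. It is also conditional: the Protocol takes the first date from a Medicare summary file and does not say that this date starts in 2014.
- *The hazard ratio is biased by a known amount in favor of ARNI.* Neither size nor direction can be derived from the document.

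What the objection does not remove is that the Protocol itself fixes the coding rule. Followed as written, no planned covariate or diagnostic would reveal an imbalance in recent infarction or stroke.

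**Conclusion.** The point holds in this limited form. For the acute Table 2 conditions, the first-date rule merges recent, recurrent and remote events, so a plausible confounder is neither matched on directly nor visible in the balance check. Exclusions and proxy covariates reduce the problem by an unknown amount. The calculated range, 0.911 to 0.986 for a true hazard ratio of 1, shows only what assumed residual prevalences of 5% vs 8–12% and multipliers of 1.5–2.5 would do. It estimates nothing about this study, and the sign could reverse. The plan contains no false statement or contradiction here. It is a covariate definition worth changing because the remedy is cheap and uses claims already held.

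**What to change.** Keep the ever-flags. For acute myocardial infarction and stroke/TIA, add an indicator for a qualifying claim in [-365, -1] days to the propensity score model and to the SMD table of every surveillance cohort. Do the same for hip/pelvic fracture and cancer where they are frequent enough. STUDY POPULATION, item 3.a, already requires continuous enrollment over the eligibility window, so these indicators have the same coverage in every interval and database.

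Report indicators for an inpatient infarction or stroke claim in the last 60 days in the balance table as well, but put them in the model only where counts allow. Models are fitted by database, interval and frailty stratum, and the rarer indicators will be sparse in some of them. With an assumed 100 patients per arm, the standard error of an SMD is about √(2/100) = 0.14, so an SMD above 0.1 on one of these in a small cohort may be chance and should be read with the counts beside it.

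The cost is a few derived variables, a few more propensity score terms and possibly slightly fewer matches in small frail cohorts.

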**Figure 2. Study design outline for comparative effectiveness and safety analysis**

## MEASUREMENTS

1. Exposure to ARNI or comparator
  - a. ARNI: sacubitril/valsartan (Entresto)
  - b. ARB (comparator): any of azilsartan, candesartan, eprosartan, Irbesartan, losartan, Olmesartan, telmisartan, valsartan
  - c. Note: prior ACEI use (commonly used for hypertension and HFrEF) is allowed. This choice will resemble a clinic situation that involves switching from ACEI to ARB or to ARNI.
  - d. Exposure risk window and gap between treatments allowed: 7 days (primary analysis) or 14 days (sensitivity analysis)

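### Drug covariates are limited to ATC3 classes screened in a general Medicare sample, so the background heart-failure drugs the protocol itself names are not guaranteed to be separately balanced

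*Protocol*

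**What the plan says.** Three parts of the protocol bear on this point.

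- **Measurements, 3. Covariates, item c** defines the drug covariates: "Prescription drugs: ATC3 classes with prevalence threshold" above 1% "in a representative Medicare sample". It lists neither the retained classes nor their members or prevalences.
- **Statistical Analysis, item 1** fits the propensity score "as a function of sociodemographic characteristics, diseases, prescription drugs, comorbidity index, and frailty index" and names no individual heart-failure drug. Balance is judged on those covariates: "We will evaluate balance in covariates using standard mean difference (<0.1 is considered adequate balance) within each surveillance cohort".
- **Background, item 3.a** quotes the guideline that renin-angiotensin inhibition "in conjunction with evidence-based beta blockers, and aldosterone antagonists in selected patients, is recommended for patients with chronic HFrEF to reduce morbidity and mortality". Measurements, 1.c adds that "prior ACEI use (commonly used for hypertension and HFrEF) is allowed", but prior ACE inhibitor use is not listed as a covariate in its own right.

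The effectiveness endpoint exposed to any resulting confounding is "Primary: a composite of all-cause death or HF hospitalization". The data come from three sources (Medicare, Optum and MarketScan), and the cohort is restricted to HFrEF.

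**The concern.** This is a non-randomised comparison, so the hazard ratio is only as good as the balance on prognostic factors. The Background describes particular companion drugs as part of care meant to lower morbidity and mortality in this disease, and it qualifies the beta blockers as evidence-based, which implies that members of the group are not interchangeable. The covariate rule works at class level and cannot make that distinction wherever a class holds both kinds of drug.

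The planned checks share the weakness. The standardised difference is computed on the same class indicators, so it can pass while the arms differ within a class. The sensitivity analyses vary only the follow-up scheme and the grace period.

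The screen raises a second problem. Prevalence in a general Medicare sample decides which classes are kept, but the classes that matter here are those used in HFrEF, in all three databases. A class concentrated in HFrEF patients can fall below 1% in a general sample and still be common in the cohort. At stake is residual confounding of the primary effectiveness endpoint that the planned diagnostics would not reveal.

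**Working it through.** The protocol gives no figure on this point, so there is nothing to reproduce. The checks below use assumed inputs, shown as ranges.

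**1. When does the 1% screen drop a class?** Let h be the HFrEF share of the Medicare sample, u the use of the class within HFrEF, and g its use outside HFrEF. The class is dropped when h·u + (1 − h)·g ≤ 0.01, that is, when u ≤ [0.01 − (1 − h)·g] / h.

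| h (assumed) | limit on u, g = 0 | g = 0.2% | g = 0.5% |
|---|---|---|---|
| 2% | 50% | 40.2% | 25.5% |
| 3% | 33.3% | 26.9% | 17.2% |
| 5% | 20% | 16.2% | 10.5% |
| 7% | 14.3% | 11.6% | 7.6% |
| 10% | 10% | 8.2% | 5.5% |

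For h = 5% and g = 0 the limit is 0.01/0.05 = 20%. For h = 5% and g = 0.5% it is (0.01 − 0.95 × 0.005)/0.05 = 10.5%. A class used by more than 1% of the sample for any reason is always kept.

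**2. Can the balance check see a gap within a class?** Suppose 60% of each arm uses the class, so the class-level standardised difference is 0. If the prognostic drug makes up 80% of class use in the ARNI arm and 70% in the ARB arm, use of that drug is 0.6 × 0.8 = 48% against 0.6 × 0.7 = 42%. Its own standardised difference is 0.06 / √[(0.48 × 0.52 + 0.42 × 0.58)/2] = 0.06/0.497 = 0.12. That exceeds the 0.1 limit while the tabulated value is 0. With shares of 75% and 70% (45% against 42%), it is 0.03 / √[(0.45 × 0.55 + 0.42 × 0.58)/2] = 0.03/0.496 = 0.06, which is within the limit.

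**3. How far could one merged class move the hazard ratio?** Let c be class use, equal in both arms. Let s1 and s0 be the shares of class use taken by the prognostic drug in the ARNI and ARB arms, and HRd that drug's effect on the composite. Other members are assumed to have no effect. The approximate multiplier on the ARNI hazard ratio is [1 − c·s1·(1 − HRd)] / [1 − c·s0·(1 − HRd)].

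- Smallest: c = 0.3, HRd = 0.85, shares 75% and 70%: 0.96625/0.96850 = 0.998.
- Middle: c = 0.6, HRd = 0.75, shares 80% and 70%: 0.880/0.895 = 0.983.
- Largest: c = 0.8, HRd = 0.65, shares 90% and 60%: 0.748/0.832 = 0.899.

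**4. How far could a dropped class move it?** Let p1 and p0 be the proportions of the ARNI and ARB arms using the class. The multiplier is [1 − p1·(1 − HRd)] / [1 − p0·(1 − HRd)].

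- Use 5% against 2%, HRd = 0.85: 0.9925/0.9970 = 0.995.
- Use 20% against 10%, HRd = 0.65: 0.930/0.965 = 0.964.

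All of these multipliers are below 1 only because the ARNI arm was assumed to have more of a beneficial drug. If the ARB arm had more, they would exceed 1.

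**The case against.** The case against has real weight.

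- **Much is already controlled.** Matching is done within six-month cohorts and by frailty status, so calendar trends are shared by both arms. The model includes chronic conditions, a comorbidity score and a frailty index. Patients with recent heart-failure hospitalisation, nursing-facility stay or renal contraindications are excluded. Classes that pass the screen are adjusted for, though coarsely. This stands, and it makes the upper end of the range less likely. None of these items, however, measures which heart-failure drug a patient takes within a class.
- **The classes and prevalences are not in the document.** This also stands. A reader might infer that important drugs are in fact dropped. The protocol identifies no such class, and one also used for common conditions would probably pass; ACE inhibitors, which the protocol calls common in hypertension, are an example. Dropping is a conditional risk.
- **The Background is easily over-read.** It recommends renin-angiotensin inhibition together with these drugs. It does not state how far outcome depends on them.
- **The size is easily overstated.** A reader might multiply several assumed imbalances and set the product against the Background's 21.8/26.5 = 0.823. That fails for three reasons. The imbalances need not all favour ARNI. The 0.823 is against enalapril, not an ARB. And a gap within a class must first be scaled by class use: with HRd = 0.70, a gap of 85% against 70% gives 0.745/0.790 = 0.943 if read as whole-cohort use, but 0.796/0.832 = 0.957 if read as shares of a class used by an assumed 80%.
- **Covariate detail may sit in an analysis plan.** A missing list would be no fault. Here the protocol states the rule itself, in terms that do not secure the balance needed.

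**Conclusion.** The point holds as a limitation of confounding control. As written, the rule does not guarantee separate balance on the background drugs the protocol singles out, its balance check cannot show an imbalance within a class, and its prevalence screen uses a general Medicare population instead of the HFrEF cohort in each database.

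The direction and size of any bias cannot be derived from the document. Under the assumed inputs, a single merged class multiplies the hazard ratio by about 0.998 to 0.90, and a dropped class by about 0.995 to 0.96. The effect runs from negligible to roughly 10%, and it favours ARNI only if ARNI starters receive more of the beneficial drug. A reader might infer that the design is biased towards ARNI, or that the safety endpoint is distorted in the same way; the protocol contains nothing that establishes either. This is a recommended improvement, with moderate confidence, and not a flaw that invalidates the comparison.

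**What to change.** In Measurements, 3.c:

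1. Keep the ATC3 classes, but apply the 1% screen in the eligible HFrEF cohort of each database.
2. Force in, regardless of prevalence, separate indicators for evidence-based beta blockers, aldosterone antagonists and prior ACE inhibitor use. Do the same for other heart-failure drugs where the ATC3 class does not isolate them. List the drugs that define each indicator in the Appendix.
3. Include each indicator in the propensity score model and in the standardised-difference table for every surveillance cohort and frailty stratum.

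The cost is small, because the indicators come from pharmacy claims the study already uses. The downside is that a few indicators may be sparse in the early, small cohorts, and slightly fewer pairs may be matched.
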